9.5.5 Endothelial Cell Count and Morphology

Endothelial cell count and morphology will be collect at Screening, Baseline, Visit 6, Visit 8, and Visit 10. Endothelial cell count will be summarized by visit, study eye/non-study eye, and treatment group. All endothelial data will be presented in subject listings.

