1. PURPOSE OF THE ANALYSES

The statistical analysis plan (SAP) contains detailed information to aid in the implementation of the statistical analysis and reporting of the study data for use in the clinical study report (CSR). This SAP is being written with due consideration of the recommendations outlined in the most recent International Conference on Harmonisation (ICH) E9 Guideline entitled Guidance for Industry: Statistical Principles for Clinical Trials and the most recent ICH E3 Guideline, entitled Guidance for Industry: Structure and Content of Clinical Study Reports.

This SAP describes the analysis sets that will be analyzed, the subject characteristics parameters, the efficacy parameters, and the safety parameters. The details of the specific statistical methods that will be used will be provided. If additional analyses are required to supplement the planned analyses described in this SAP, they may be completed and will be identified in the CSR. Table, figure, and listing specifications are provided in separate documents.

Please note that text within the SAP that comes directly from the protocol will be shown in italics.

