3. GENERAL ANALYSIS AND REPORTING CONVENTIONS

The following is a list of general analysis and reporting conventions to be applied for this study.

- Categorical variables will be summarized using counts (n) and percentages (%) and will be presented in the form "n (xx.x)". To ensure completeness, summaries for categorical and discrete variables will include all categories, even if no subjects had a response in a particular category.
- Continuous variables will be summarized using mean, standard deviation (SD), minimum, maximum, median, and number of subjects. The mean and median will be reported to one more level of precision than the original observations, and the SD will be reported to 2 more levels of precision than the original observations. The minimum and maximum will be the same precision as the original data.
- All exploratory statistical tests will be 2-sided and nominal significance will be determined at the 0.05 level. All p-values will be rounded to 3 decimal places; p-values that round to "0.000" will be presented as "< 0.001".
- All analyses will be performed using SAS® System version 9.2 or higher.
- Dates will be displayed as ddmmmyyyy (e.g., 24Jan2005).

Since this study has not been powered to allow formal hypothesis testing of toxicity rates or efficacy between dose groups, any examination of treatment differences will be exploratory in nature. For all analyses, subject-level covariates will be summarized within each group by treatment (Table 2). Eye-level covariates will be summarized for each cell in the final row of Table 3.

Table 2:Subject-Level Analyses

Group 1	Group 2	Group 3	Group 4
2 implants ENV515-3	3 implants ENV515-3	1 implant ENV515-1	2 implants ENV515-1
(28.2 µg travoprost)	(42.3 µg travoprost)	(42.5 µg travoprost)	(85.0 µg travoprost)

Table 3:Eye-Level Analyses

Group 1			Group 2	Group 3		Group 4	
2 implan	2 implants ENV515-3 3 implants ENV515-3		1 implant ENV515-1		2 implants ENV515-1		
(28.2 µg	(28.2 µg travoprost)		(42.3 µg travoprost)		(42.5 µg travoprost)		g travoprost)
ENV515-3	TRAVA-TAN Z	ENV515-3	TRAVA-TAN	ENV515-1	TRAVA-TAN Z	ENV515-	TRAVA-TAN
SE	NSE	SE	Z NSE	SE	NSE	1 SE	Z NSE

SE: Study eye; NSE: Non-study eye

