11. LIST OF PLANNED TABLES

Rho Table Identifier	Table No.	Title	Population
DS_TAA	1	Summary of Subject Disposition by Treatment Group	All Subjects
DM_TAA	2	Summary of Demographic and Baseline Characteristics by Treatment Group	Safety
DM_TAB	3	Summary of Disease Baseline Clinical Characteristics by Treatment Group	Safety
EF_TAA	4	Summary of Change from Baseline Average Intraocular Pressure Diurnal Measurement by Treatment Group	ITT
EF_TAB	5	Summary of Change from Baseline Average Intraocular Pressure Diurnal Measurement by Treatment Group	Per Protocol
EF_TAC	6	Summary of percent Change from Baseline Average Intraocular Pressure Diurnal Measurement by Treatment Group	ITT
EF_TAD	7	Summary of percent Change from Baseline Average Intraocular Pressure Diurnal Measurement by Treatment Group	Per Protocol
EF_TAE	8	Analysis of Change from Baseline Average Intraocular Pressure Diurnal measurement	ITT
EF_TAF	9	Analysis of Change from Baseline Average Intraocular Pressure Diurnal measurement	Per Protocol

Envisia Therapeu Protocol No. ENV		CONFIDENTIAL	Statistical Analysis Plan 23SEP2015
EF_TAG	10	Summary of Change from Baseline Average Intraocular Pressure Diurnal Measurement by Treatment Group – Subjects with High Baseline IOP	ITT
EF_TAH	11	Summary of Change from Baseline Average Intraocular Pressure Diurnal Measurement by Treatment Group – Subjects with Low Baseline IOP	Per Protocol
EF_TAI	12	Summary of Change form Baseline Intraocular Pressure Diurnal Measurements by Treatment Group and Time	ITT
EF_TAJ	13	Summary of Percent Change from Baseline Intraocular Pressure Diurnal Measurements by Treatment Group and Time	ITT
EF_TAK	14	Analysis of Change from Baseline Intraocular Pressure Diurnal Measurements by Treatment Group and Time	ITT
EF_TAL	15	Summary of Change from Baseline Intraocular Pressure at 8 AM by Treatment Group and Visit	ITT
EF_TAM	16	Summary of Percent Change from Baseline Intraocular Pressure at 8 AM by Treatment Group and Visit	ITT
EF_TAN	17	Analysis of Change from Baseline Intraocular Pressure at 8 AM by Treatment Group and Time	ITT
EF_TAO	18	Analysis of Change from Baseline Average Intraocular Pressure Diurnal measurement for Study Eye vs Non-Study Eye	ITT
EF_TAP	19	Analysis of Change from Baseline Intraocular Pressure	ITT

Subjects with Treatment Emergent Adverse Events by Treatment Group, System Organ Class, and Preferred Term – Study Eye	Statistica

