Envisia Therapeutics Protocol No. ENV515-01		CONFIDENTIAL		Statistical Analysis Plan 23SEP2015
		Urinalysis Values: Shift from Baseline to Each Visit by Treatment Group		
CT_TAA	47	Mean and Mean Change from Baseline in Corneal Thickness by Treatment Group and Visit	Safety	
EC_TAA	48	Mean and Mean Change from Baseline in Endothelial Cell Count by Treatment Group and Visit	Safety	
SL_TAA	49	Summary of Change from Baseline in Hyperemia Score by Treatment Group and Visit	Safety	
SL_TAB	50	Shift from Baseline in Slit Lamp Biomicroscopy by Visit and Treatment Group	Safety	
DF_TAA	51	Shift from Baseline in Dilated Fundus Exam Finding to Each Visit by Treatment Group	Safety	
VF_TAA	5	Shift from Baseline in Visual Field to Each Visit by Treatment Group	Safety	
VA_TAA	53	Mean and Mean Change from Baseline in Visual Acuity (EDTRS Letters Missed)) by Treatment Group and Visit	Safety	
VA_TAB	54	Proportion of Subjects with 3 or More Lines Lost by Treatment Group	Safety	
PM_TAA	55	Mean and Mean Change from Baseline in Pupil Measurement by Treatment Group and Visit	Safety	
PK_TAA	56	Summary of Pharmacokinetics and Implant Information by Treatment Group	Safety	

ŝ

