12. LIST OF PLANNED DATA LISTINGS

Listing No.	Title
-------------	-------

- 1 Subject Disposition
- 2 Protocol Deviations
- 3 Demographics
- 4 Baseline Clinical Characteristics
- 5 Intraocular Pressure Measurement
- 6 Travoprost Implant Exposure
- 7 Adverse Events
- 8 Hematology Results
- 9 Chemistry Results
- 10 Urinalysis Results
- 11 Vital Signs
- 12 Physical Examinations
- 13 Pachymetry
- 14 Visual Acuity
- 15 Endothelial Cell Count and Morphology
- 16 Slit Lamp Biomicroscopy
- 17 Pupil Measurements
- 18 Dilated Fundus Examination
- 19 Visual Field
- 20 Anterior Segment
- 21 Goinoscopy
- 22 Pharmacokinetics

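### SAP (2015, Cohort 1) 9.5.5 puts the last endothelial cell count at Visit 10 where the protocol takes it at Visit 11, and no planned table title counts eyes with more than 10% loss

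*SAP*

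**What the plan says.** The SAP document holds two plans. This point concerns the 2015 plan for Cohort 1.

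- Section 9.5.5 sets the visits: "Endothelial cell count and morphology will be collect at Screening, Baseline, Visit 6, Visit 8, and Visit 10". It then sets the output: "Endothelial cell count will be summarized by visit, study eye/non-study eye, and treatment group", and "All endothelial data will be presented in subject listings".
- The only endothelial entry in the list of planned tables (section 11) is Table 48, "Mean and Mean Change from Baseline in Endothelial Cell Count by Treatment Group and Visit". The only listing (section 12) is Listing 15, "Endothelial Cell Count and Morphology".
- Section 3 fixes the statistics: "Continuous variables will be summarized using mean, standard deviation (SD), minimum, maximum, median, and number of subjects".
- Section 1 says that "Table, figure, and listing specifications are provided in separate documents", so the table shells cannot be checked here.

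On the protocol side, 4.4.1 lists a fall of more than 10% in central endothelial cell density among reasons for which the investigator may withdraw a Cohort 1 patient. Section 18.1.2 asks for descriptive statistics and patient listings of the safety measures. Section 1.4.3 reports two affected patients, both in the three-implant ENV515-3 arm. One had an SAE. The other lost more than 10% of baseline but was not classed as having an AE.

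**The concern.** Safety and tolerability are a primary objective of Cohort 1, and the dose arms have 2 to 10 study eyes. The protocol's endothelial conclusion is a count of cases by arm: two with three implants, none in the other arms (1.4.3, 1.6). It adds that the loss did not advance once the implants were out. The first statement needs a per-eye count, and the second needs the count taken after explantation. Section 9.5.5 names a visit at which that post-explant count is not scheduled, and none of the planned table titles gives the per-eye count.

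**Working it through.** **Visits.** The protocol sources are the Table 1 row for specular microscopy and the visit procedures in 5.10 and 5.11.

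| Source | Screening (V1) | Baseline (V2) | V6 | V8 | V10 | V11 |
|---|---|---|---|---|---|---|
| SAP 9.5.5 | yes | yes | yes | yes | yes | no |
| Protocol Table 1 | yes | yes | yes | yes | no | yes |
| Protocol 5.10 / 5.11 | | | | | not among the 14 steps | step 5 |

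Implants come out at Visit 9 (Day 28), so Visit 11 (Day 42 to 49) is the only scheduled count afterwards. Visit 10 is correct for pachymetry and pupil measurement (SAP 9.5.3 and 9.5.7). The SAP's own schedule (13.1) is cut off after Visit 8 in the available text, so it cannot settle the matter.

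**Table titles.** Table 48 names mean and mean change. No title names percent change in cell count or eyes past a loss threshold. The same list does both elsewhere. Percent change is named for IOP in Tables 6, 7, 13 and 16 (Table 16: "Summary of Percent Change from Baseline Intraocular Pressure at 8 AM by Treatment Group and Visit"), and Table 54 gives a threshold proportion for visual acuity.

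**What the arm mean would show.** Assume two of ten eyes lose L% and eight are unchanged. Arm mean percent change = −(2 × L)/10. At an assumed common baseline of 2500 cells/mm²:

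| L | Mean % change | Mean change, cells/mm² |
|---|---|---|
| 11% | −2.2% | −55 |
| 15% | −3.0% | −75 |
| 20% | −4.0% | −100 |
| 30% | −6.0% | −150 |

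**What the other Table 48 statistics add.** The minimum shows the worst eye. A 10% loss is 200, 250 or 300 cells/mm² at baselines of 2000, 2500 or 3000. If the 2000 entry floor (protocol 4.1) still holds at baseline, a worst change of no more than 200 rules out any eye above 10%. Beyond 200, absolute change alone does not decide it.

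The minimum does not by itself show a second eye. With assumed losses of 30% and 11% and eight eyes at zero, the mean is (−30 − 11)/10 = −4.1% and the minimum is −30%.

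The SD and maximum help. Take two eyes at −375 and eight at 0:

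- Mean = −750/10 = −75.
- Sum of squares = 2 × 375² = 281,250.
- SD = √[(281,250 − 10 × 75²)/9] = √25,000 = 158.1.
- Minimum −375, maximum 0.

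Remove the minimum, and the other nine eyes sum to −375 with sum of squares 140,625 = 375². As none is above zero, exactly one of them is −375. In this idealised case the second eye can be recovered. With ordinary measurement noise the recovery would be imprecise.

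**What a threshold table would show.** Arm sizes are 7, 10, 2 and 2 (protocol 1.3, Table 9). Clopper–Pearson 95% limits are the 0.025 quantile of Beta(x, n − x + 1) and the 0.975 quantile of Beta(x + 1, n − x). For x = 0 the upper limit is 1 − 0.025^(1/n).

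- Three-implant arm, threshold table: 2/10 = 20% (2.5% to 55.6%). This takes the SAE eye as above 10%, which 1.4.3 implies but does not quantify.
- Same arm, AE tables only: 1/10 = 10% (0.3% to 44.5%).
- Other arms, reading the reported absence of impact as no eye above 10%: 0/7, upper limit 1 − 0.025^(1/7) = 41%; 0/2 twice, upper limit 1 − 0.025^(1/2) = 84%.

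**The case against.** The visit mismatch is not in dispute; its consequence is. Section 9.5.5 summarises by visit without confining the table to the visits it lists, and Table 48 is titled by visit. A programmer working from the data could include Visit 11 anyway. The protocol governs collection, and 1.4.3 did report on progression after explantation. A reader might infer that the statement on progression has no data behind it. The documents do not support that: they show a wrong label in the plan, not a missing measurement.

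On the threshold table, the case against is that this is preference. Protocol 18.1.2 asks for descriptive statistics and listings, and Table 48 with Listing 15 supplies both. The 10% figure is one item in a discretionary, open-ended withdrawal list, not an endpoint. SAP 9.3 has other significant events summarised individually in the CSR, so the second eye could be described there. The medical monitor reviewed ocular safety data as they arose, and a listing of 21 patients is short. In the two arms of two eyes, minimum and maximum give both values. Percent change may also be in shells that cannot be seen.

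Most of this stands. It defeats two stronger readings that a reader might draw: that the SAP breaches the protocol, and that the second eye was concealed or could be found nowhere but the listing. It does not supply a planned table with the per-eye count. A narrative under 9.3 is possible but not certain, and recovery from the SD needs near-noiseless data.

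**Conclusion.** Two modest points hold. First, 9.5.5 names the wrong visit for the last cell count. Read literally, it plans a summary at Visit 10, where no count is scheduled, and leaves out Visit 11, the only scheduled post-explant count. This rests on the protocol text alone.

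Second, an eye with more than 10% loss that is not coded as an AE is counted in no titled table. It would be found in Listing 15, or possibly in a CSR narrative. For Cohort 1 the difference is 2/10 against 1/10 in the three-implant arm, if the SAE eye also exceeded 10%. The intervals overlap widely, so the gain is the count itself, not a comparison. The dilution figures rest on assumed losses, eight unchanged eyes and a 2500 baseline. This second point is a worthwhile improvement in display rather than an error, and it is subject to the unseen shells.

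**What to change.** - In SAP 9.5.5, change Visit 10 to Visit 11 for endothelial cell count. Show that visit separately, because it follows cataract surgery as well as implant removal.
- Add percent change from baseline in cell count.
- Add one descriptive table of the number and percentage of eyes with more than 10% decrease, by dose group and by study and non-study eye, at Visits 6 and 8 and at the worst value while the implant was in place. Exact intervals are optional and uninformative in the arms of two eyes.

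The cost is a one-word correction, a percent-change summary and one extra table, from data already in Listing 15. SAP section 1 allows supplementary analyses if they are identified in the CSR. The drawback for the sponsor is a slightly less favourable display: 2/10 rather than 1/10 in the three-implant arm, on the assumption above.

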9.5.6 Slit Lamp Biomicroscopy Exams

Slit lamp biomicroscopy exams, including corneal staining, will be performed at all study visits. Summary shift tables will be presented by visit, study eye/non-study eye, and treatment. In addition, hyperemia mean and mean change from baseline will be summarized in a table. All slit lamp biomicroscopy findings will be listed.

.

9.5.7 Pupil Measurements

Pupil Measurements are done at Screening, Baseline, Visit 6, Visit 8 and Visit 10. Pupil measurements will be summarized by visit, study eye/non-study eye, and treatment group. All pupil measurement data will be listed.

9.5.8 Binocular Indirect Ophthalmoscopy (Dilated Fundus Exam)

A dilated fundus exam will performed at the Screening Visit, Baseline visit, Visit 6, Visit 8, and Visit 10. Shift tables of normal/abnormal findings will be presented by visit, study eye/non-study eye, and treatment group. All dilated fundus exam data will be listed.

9.5.9 Visual Field

Visual field assessments will be made at the Screening Visit and Visit 10. Shift tables of normal/abnormal findings will be presented by study eye/non-study eye and treatment group. All visual field data will be listed.

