- 8. Have severe glaucoma with a mean defect (MD) worse than -8.0, central island of vision, or otherwise severe glaucoma that would not tolerate a possible short-term increase in IOP.
- 9. According to the investigator's best judgment, are at risk for progression of glaucoma, VF or VA worsening as a consequence of participation in the trial.
- 10. Have any abnormality preventing reliable applanation tonometry in either eye.
- 11. Have any corneal opacity or are uncooperative in such a way that restricts adequate examination of the ocular fundus or anterior chamber in either eye.
- 12. Are unwilling to discontinue use of contact lenses at least 2 days prior to Visit 2 for soft lenses and at least 7 days prior to Visit 2 for rigid gas permeable (RGP) lenses through completion of the study at Visit 11.
- 13. Have progressive retinal or optic nerve disease apart from glaucoma.
- 14. Have any clinically significant, serious, or severe medical or psychiatric condition.

- 15. Are, in the opinion of the investigator, unable or unwilling to comply with study procedures, including attending the scheduled study visits.
- 16. Have a history, or a suspected history of drug or alcohol dependence in the preceding year.
- 17. Are unwilling to limit alcohol ingestion and smoking for the 8-hour period prior to and during study appointments after Visit 1.
- 18. Have received any investigational product within the past 30 days prior to Visit 1.
- 19. Have any history of allergic hypersensitivity or poor tolerance to any components of the preparations used in this trial such as travoprost or PLA excipients.
- 20. Have a history of insufficient response to PGA topical treatment, i.e., are PGA non-responders.
- 21. Are an employee of the clinical site that is directly involved in the management, administration, or support of this study or are an immediate family member of the same.
- 22. Have a central corneal thickness greater than 600 micrometers as determined by pachymetry at the Baseline Visit (Visit 2).
- 23. Had prior intraocular surgery or any ocular or systemic condition that may confound the study outcome per the investigator's recommendation.

4.3. Randomization Criteria, Cohort 1

At the Randomization Visit (Visit 3/Day 1), an eligible patient must:

• Continue to meet all inclusion/exclusion criteria as defined in Sections 4.1 and 4.2

4.4. Patient Withdrawal Criteria, Cohort 1

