15.1.4. Binocular Indirect Ophthalmoscopy (Dilated Fundus Exam) Guidelines

Dilated ophthalmoscopy will be performed according to the investigator's preferred procedure. This procedure will be the same for all patients observed at an investigator's site. Observations should be graded as normal or abnormal. All findings should be noted and specified as clinically significant or not clinically significant and graded for severity on a 0 - 5 scale. The fundus will be examined thoroughly and the following variables examined:

- Retina
- Macula
- Choroid
- Vitreous
- Optic nerve/disc
- Cup/disc ratio

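### In the Cohort 1 SAP the only summary tables for fundus and visual field are normal/abnormal shifts, so worsening in an eye already abnormal at baseline is tabulated the same as no change

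*SAP*

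**What the plan says.** The 2015 SAP for Cohort 1 treats the two examinations alike.

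- **Visual field (9.5.9).** "Visual field assessments will be made at the Screening Visit and Visit 10". The summary is: "Shift tables of normal/abnormal findings will be presented by study eye/non-study eye and treatment group". The section ends: "All visual field data will be listed".
- **Dilated fundus exam (9.5.8).** Done at Screening, Baseline and Visits 6, 8 and 10. The summary is: "Shift tables of normal/abnormal findings will be presented by visit, study eye/non-study eye, and treatment group". The section ends: "All dilated fundus exam data will be listed".
- **Planned tables (section 11).** There is one table for each: DF_TAA for the fundus and VF_TAA, titled "Shift from Baseline in Visual Field to Each Visit by Treatment Group", for the field. No table covers mean defect, the fundus severity grade or the cup/disc ratio.
- **Planned listings (section 12).** Listing 18 is the fundus exam and Listing 19 the visual field.

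The protocol has finer information recorded. For the fundus, section 15.1.4 says: "All findings should be noted and specified as clinically significant or not clinically significant and graded for severity on a 0 - 5 scale". It names six variables, including the optic nerve/disc and the cup/disc ratio. The field is tested on the Humphrey analyser with program 24-2 (15.1.10), and mean defect is used for eligibility (4.2, exclusion 8). Section 18.1.2 asks for changes in both examinations to be summarised and compared descriptively, across study arms for Cohort 1.

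**The concern.** A two-level shift table suits a population that starts normal. Cohort 1 is mixed: bilateral ocular hypertension or mild to moderate open-angle glaucoma (Protocol 4.1). Section 3 defines early glaucoma by focal rim thinning, with or without a small field defect, and a mean defect is excluded only when worse than -8.0. Glaucomatous discs, and some fields, are therefore abnormal before the implant goes in.

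The protocol takes progression seriously. Exclusion 9 removes patients who, in the investigator's judgment, "are at risk for progression of glaucoma, VF or VA worsening as a consequence of participation in the trial", and section 4.4.1 lists disc rim pallor among possible safety reasons for withdrawal. Yet in eyes that already have disease, the tables cannot show that it has advanced. A reader of the study report who sees no shifts could take that as no worsening.

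Other sections of the same SAP go further. Section 9.5.6 adds mean change in hyperemia beside the slit-lamp shift tables, and 9.5.3 summarises change in corneal thickness.

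**Working it through.** The plan states no figure on this point, so there is none to reproduce. The check is one of structure, followed by an illustration on assumed values.

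**Step 1: what the table can hold.** Suppose *b* eyes are normal and *a* eyes abnormal at baseline. Let *k* of the abnormal eyes worsen, and let nothing else change.

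| Baseline to follow-up | Count if k = 0 | Count if k = a |
|---|---|---|
| Normal to normal | b | b |
| Normal to abnormal | 0 | 0 |
| Abnormal to normal | 0 | 0 |
| Abnormal to abnormal | a | a |

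The table is identical for every *k* from 0 to *a*. It carries no information on worsening among eyes abnormal at baseline.

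**Step 2: how far this reaches.** An ocular hypertension eye with a normal disc and field can still move to abnormal. For the fundus, the SAP text does not say whether the shift is made per structure or for the whole eye. If per structure, a new macular finding in an eye with a thinned rim would register, and only worsening within an already abnormal structure is lost. If for the whole eye, both are lost.

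**Step 3: what the baseline is.** SAP 9.1 sets baseline as the last measurement before the implant unless otherwise noted. The fundus is examined at Visit 2, after washout, so its shift covers the period from just before implantation. The field is tested only at Screening and Visit 10, so its change spans washout and treatment and, in the study eye, cataract removal at Visit 9. Fundus exams at Visits 6 and 8 precede surgery in both eyes.

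**Step 4: illustration.** Let *n* be the number of study eyes, *w* the true proportion that worsen and *q* the proportion abnormal at baseline. Assume that worsening is independent between eyes and equally likely whatever the baseline status, and that every normal eye that worsens is rated abnormal. The chance that the shift table shows at least one worsened eye is

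P = 1 - [1 - w(1 - q)]^n.

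Neither *w* nor *q* is in the documents, so *w* is set at 10% and *q* runs over its whole range. Group sizes are from Protocol 1.4.1 (21 in all; 10 and 7 on ENV515-3; 2 and 2 on ENV515-1). Example: n = 21 and q = 50% give w(1 - q) = 0.05, and 1 - 0.95^21 = 0.66.

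| n | q = 0 | 25% | 50% | 75% | 100% |
|---|---|---|---|---|---|
| 21 | 0.89 | 0.81 | 0.66 | 0.41 | 0 |
| 10 | 0.65 | 0.54 | 0.40 | 0.22 | 0 |
| 7 | 0.52 | 0.42 | 0.30 | 0.16 | 0 |

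These values show direction and steepness. They do not estimate what happened in this trial.

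**The case against.** The strongest reply is that nothing is withheld. All fundus and field data are listed, and 21 patients can be read eye by eye. Treatment-emergent adverse events are tabulated by eye, intensity and relationship, and withdrawals due to adverse events are summarised individually (SAP 9.3). Reasons for discontinuation are tabulated by dose group (5.1). The study is unpowered and its comparisons exploratory, the protocol asks only for descriptive statistics, and SAP section 1 allows further analyses identified in the study report.

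Much of this stands. A reader might infer that the SAP does not report worsening in these eyes at all; the listings rule that out. The other routes are partial. A listing does not set eyes or dose groups side by side as Protocol 18.1.2 asks. An adverse event appears only if the investigator records one, and Protocol 17.3 defines a threshold in advance only for endothelial cell loss, not for field or disc change. Protocol 1.4.1 reports no early discontinuations in Cohort 1, so that table adds nothing here.

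A reader might also infer that the two-level fundus table conceals harm from washout. It does not: the fundus baseline is taken after washout, so no scale would show such harm.

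A third objection is that a mean defect summary can mislead. Visit 10 follows cataract removal in the study eye, and Protocol 15.1.10 permits more than one test strategy without requiring the same one at both visits. This stands, and it limits the remedy.

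**Conclusion.** The point holds for the summary tables of the 2015 Cohort 1 SAP. In DF_TAA and VF_TAA, worsening in an eye already abnormal at baseline cannot be told from stability. It has to be sought in Listings 18 and 19 or in the adverse event tables.

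Its size cannot be fixed. The split between ocular hypertension and glaucoma, and the share of discs and fields abnormal at baseline, are not given. It is tempting to say that nearly all disc worsening is hidden. The definition of early glaucoma suggests this for glaucomatous discs if the optic nerve is rated simply normal or abnormal, but it does not carry over to ocular hypertension eyes or to fields, since the same definition includes eyes without field change.

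This is a modest reporting weakness that is cheap to mend. It does not affect the IOP analyses.

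**What to change.** - **SAP 9.5.8.** Present shifts in the recorded 0-5 severity grade for each structure, and change from baseline in cup/disc ratio, by eye, visit and dose group. State that these measure change after implantation, not the effect of washout.
- **SAP 9.5.9.** Keep the shift table. Add change from Screening to Visit 10 in Humphrey mean defect, by eye, if it was captured at Visit 10. The documents do not confirm that it was, so the sponsor should check. Footnote the study-eye result: the visit follows cataract removal and the test strategy may differ between visits. The fellow eye, which has no surgery, is the cleaner reading.

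Cohort 1 is complete, so label the additions supplementary and identify them in the study report, as SAP section 1 allows. They need no new visits or procedures. The cost is some extra table programming and the risk that the study-eye mean defect is over-read if the footnote is dropped. No clinical rule changes.
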